11.3.4. Disease Activity Index

Disease Activity Index		
ESSDAI		

The European League Against Rheumatism (EULAR) Sjögren's syndrome disease activity index (ESSDAI) is a systemic disease activity index that was designed to measure disease activity in patients with primary SS. The ESSDAI is a disease activity index that was generated in 2009, by consensus of a large group of worldwide experts from European and North American countries. The ESSDAI is a systemic disease activity index and includes 12 domains (i.e., organ systems; cutaneous, respiratory, renal, articular, muscular, peripheral nervous system (PNS), central nervous system (CNS), haematological, glandular, constitutional, lymphadenopathic, biological). Each domain is divided in three to four levels depending on their degree activity. The final score, the sum of all domain scores (given below), falls between 0 and theoretically 123, with 0 being no disease activity and 123 being most severe disease activity.
		
Domain	Activity level	Description
Constitutional - Exclusion of fever of infectious origin and voluntary weight loss	No=0	Absence of the following symptoms
	Low=3	Mild or intermittent fever (37.5°–38.5°C)/night sweats and/or involuntary weight loss of 5–10% of body weight
	Moderate=6	Severe fever (>38.5°C) / night sweats and/or involuntary weight loss of >10% of body weight
Lymphadenopathy - Exclusion of infection	No=0	Absence of the following features
	Low=4	Lymphadenopathy ≥ 1 cm in any nodal region or ≥ 2 cm in inguinal region
	Moderate=8	Lymphadenopathy ≥ 2 cm in any nodal region or ≥ 3 cm in inguinal region, and/or splenomegaly (clinically palpable or assessed by imaging)
	High=12	Current malignant B-cell proliferative disorder*
Glandular - Exclusion of stone or infection	No=0	Absence of glandular swelling
	Low=2	Small glandular swelling with enlarged parotid (≤ 3 cm), or limited submandibular or lachrymal swelling
	Moderate=4	Major glandular swelling with enlarged parotid (>3 cm), or important submandibular or lachrymal swelling

Disease Activity Index		
Articular - Exclusion of osteoarthritis	No=0	Absence of currently active articular involvement
	Low=2	Arthralgias in hands, wrists, ankles and feet accompanied by morning stiffness (>30 min)
	Moderate=4	1–5 (of 28 total count) synovitis
	High=6	≥6 (of 28 total count) synovitis
Cutaneous - Rate as ‘No activity’ stable long-lasting features related to damage	No=0	Absence of currently active cutaneous involvement
	Low=3	Erythema multiforma
	Moderate=6	Limited cutaneous vasculitis, including urticarial vasculitis, or purpura limited to feet and ankle, or subacute cutaneous lupus
	High=9	Diffuse cutaneous vasculitis, including urticarial vasculitis, or diffuse purpura, or ulcers related to vasculitis
Pulmonary - Rate as ‘No activity’ stable long-lasting features related to damage, or respiratory involvement not related to the disease (tobacco use, etc.)	No=0	Absence of currently active pulmonary involvement
	Low=5	Persistent cough or bronchial involvement with no radiographic abnormalities on radiography Or radiological or HRCT evidence of interstitial lung disease with: No breathlessness and normal lung function test.
	Moderate=10	Moderately active pulmonary involvement, such as interstitial lung disease shown by HRCT with shortness of breath on exercise (NHYA II) or abnormal lung function tests restricted to: $70\% > DL_{CO} \geq 40\%$ or $80\% > FVC \geq 60\%$
	High=15	Highly active pulmonary involvement, such as interstitial lung disease shown by HRCT with shortness of breath at rest (NHYA III, IV) or with abnormal lung function tests: $DL_{CO} < 40\%$ or $FVC < 60\%$

Disease Activity Index		
Renal - Rate as 'No activity' stable long-lasting features related to damage, and renal involvement not related to the disease. If biopsy has been performed, please rate activity based on histological features first	No=0	Absence of currently active renal involvement with proteinuria <0.5 g/day, no haematuria, no leucocyturia, no acidosis, or long-lasting stable proteinuria due to damage
	Low=5	Evidence of mild active renal involvement, limited to tubular acidosis without renal failure or glomerular involvement with proteinuria (between 0.5 and 1 g/day) and without haematuria or renal failure (GFR ≥60 mL/min)
	Moderate=10	Moderately active renal involvement, such as tubular acidosis with renal failure (GFR <60 mL/min) or glomerular involvement with proteinuria between 1 and 1.5 g/day and without haematuria or renal failure (GFR ≥60 mL/min) or histological evidence of extra-membranous glomerulonephritis or important interstitial lymphoid infiltrate
	High=15	Highly active renal involvement, such as glomerular involvement with proteinuria >1.5 g/day or haematuria or renal failure (GFR <60 mL/min), or histological evidence of proliferative glomerulonephritis or cryoglobulinemia related renal involvement
Muscular - Exclusion of weakness due to corticosteroids	No=0	Absence of currently active muscular involvement
	Low=6	Mild active myositis shown by abnormal EMG or biopsy with no weakness and creatine kinase (N<CK≤2N)
	Moderate=12	Moderately active myositis proven by abnormal EMG or biopsy with weakness (maximal deficit of 4/5), or elevated creatine kinase (2N <CK ≤4N),
	High=18	Highly active myositis shown by abnormal EMG or biopsy with weakness (deficit ≤3/5) or elevated creatine kinase (>4N)

Disease Activity Index		
PNS - Rate as 'No activity' stable long-lasting features related to damage or PNS involvement not related to the disease	No=0	Absence of currently active PNS involvement
	Low=5	Mild active peripheral nervous system involvement, such as pure sensory axonal polyneuropathy shown by NCS or trigeminal (V) neuralgia
	Moderate=10	Moderately active peripheral nervous system involvement shown by NCS, such as axonal sensory-motor neuropathy with maximal motor deficit of 4/5, pure sensory neuropathy with presence of cryoglobulinemic vasculitis, ganglionopathy with symptoms restricted to mild/moderate ataxia, inflammatory demyelinating polyneuropathy (CIDP) with mild functional impairment (maximal motor deficit of 4/5 or mild ataxia),
		Or cranial nerve involvement of peripheral origin (except trigeminal (V) neuralgia)
High=15	Highly active PNS involvement shown by NCS, such as axonal sensory-motor neuropathy with motor deficit $\leq 3/5$, peripheral nerve involvement due to vasculitis (mononeuritis multiplex, etc), severe ataxia due to ganglionopathy, inflammatory demyelinating polyneuropathy (CIDP) with severe functional impairment: motor deficit $\leq 3/5$ or severe ataxia	
CNS - Rate as 'No activity' stable long-lasting features related to damage or CNS involvement not related to the disease	No=0	Absence of currently active CNS involvement
	Moderate=10	Moderately active CNS features, such as cranial nerve involvement of central origin, optic neuritis or multiple sclerosis-like syndrome with symptoms restricted to pure sensory impairment or proven cognitive impairment

Disease Activity Index		
	High=15	Highly active CNS features, such as cerebral vasculitis with cerebrovascular accident or transient ischaemic attack, seizures, transverse myelitis, lymphocytic meningitis, multiple sclerosis-like syndrome with motor deficit.
Haematological - For anaemia, neutropenia, and thrombopenia, only autoimmune cytopenia must be considered Exclusion of vitamin or iron deficiency, drug-induced cytopenia	No=0	Absence of autoimmune cytopenia
	Low=2	Cytopenia of autoimmune origin with neutropenia (1000<neutrophils<1500/mm ³), and/or anaemia (10<haemoglobin<12 g/dL), and/or thrombocytopenia (100 000<platelets<150 000/mm ³) Or lymphopenia (500<lymphocytes<1000/mm ³)
	Moderate=4	Cytopenia of autoimmune origin with neutropenia (500≤neutrophils≤1000/mm ³), and/or anaemia (8≤haemoglobin≤10 g/dL), and/or thrombocytopenia (50 000≤platelets≤100 000/mm ³) Or lymphopenia (≤500/mm ³)
	High=6	Cytopenia of autoimmune origin with neutropenia (neutrophils <500/mm ³), and/or or anaemia (haemoglobin <8 g/dL) and/or thrombocytopenia (platelets <50 000/mm ³)
Biological	No=0	Absence of any of the following biological features
	Low=1	Clonal component and/or hypocomplementemia (low C4 or C3 or CH50) and/or hypergammaglobulinemia or high IgG level between 16 and 20 g/L
	Moderate=2	Presence of cryoglobulinemia and/or hypergammaglobulinemia or high IgG level >20 g/L, and/or recent onset hypogammaglobulinemia or recent decrease of IgG level (<5 g/L)

Disease Activity Index

ESSPRI

The EULAR Sjögren’s syndrome patient reported index (ESSPRI) was developed as a simple index for measuring pSS patient’s symptoms. The ESSPRI is calculated by averaging the scales for pain, fatigue and dryness (Cho et al., 2013). The final ESSPRI score is therefore continuous and ranges from 0 to 10 with 10 being maximal pSS symptoms.

1) How severe has your dryness been during the last 2 weeks ?

No dryness												Maximal imaginable dryness
	0	1	2	3	4	5	6	7	8	9	10	

2) How severe has your fatigue been during the last 2 weeks ?

No fatigue												Maximal imaginable fatigue
	0	1	2	3	4	5	6	7	8	9	10	

3) How severe has your pain (joint or muscular pains in your arms or legs) been during the last 2 weeks ?

No pain												Maximal imaginable pain
	0	1	2	3	4	5	6	7	8	9	10	

Seror R et al. Ann Rheum Dis doi:10.1136/annrheumdis-2013-204615

11.3.5. Histology

Histology	

Two types of histology analysis will be conducted:
 
 1. H&E 2. Immune Histochemistry (IHC) 
Each analysis will be performed by two operators (blinded to the outcome of other’s assessments). Average values will be calculated and reported.
 
The following parameters will be collected:
 
 • Focus Score • Volume Fraction • CD3/CD20 (T cell / B cell; double staining) • CD21 (Germinal Centres) • CD138 (plasma cells) • IgG (B cell activity) • IgM (B cell activity) • IgA (B cell activity) • Ki67 (proliferation) 	

} H&E
	
} Immune Histochemistry (IHC)

Volume fraction = aggregate area / total glandular area
	

11.3.6. Laboratory Biomarkers of Disease Activity

Laboratory Biomarkers of Disease Activity

Laboratory Biomarkers of Disease Activity include (LBTESTCD):
 
 • Serum bicarbonate (LBTESTCD=HC03_PLC) • Serum chloride (LBTESTCD=CL_PLC) • Cryoglobulin (LBTESTCD=CYRO_PLG) • Urinary Protein creatinine ratio (PRTCRT_URQ) • Total Immunoglobulin (LBTESTCD=IG-PLC) • IgG (LBTESTCD=IGG_PLC) • IgA (LBTESTCD=IGA_PLC) • IgM (LBTESTCD=IGM_PLC) • Serum Monoclonal Protein – Electrophoresis (LBTESTCD=MPROTE_PLC) • Complement component 3 (LBTESTCD=C3_PLC) • Complement component 4 (LBTESTCD=C4_PLC)

- Anti-Sjogrens-syndrome-related antigen A (qualitative) (LBTESTCD=SJSSAA_PLG)
- Anti-Sjogrens-syndrome-related antigen B (qualitative) (LBTESTCD=SJSSAB_PLG)
- Serum creatinine (LBTESTCD=CRT_PLC)
- Urea/BUN (LBTESTCD=UREA_PLC)
- Glomerular filtration rate (MDRD)
- Creatine kinase (LBTESTCD=CK_PLC)
- Haemoglobin (LBTESTCD=HB_PLC)
- White blood cell count (LBTESTCD=WBC_PLC)
- Neutrophil count (LBTESTCD=NEUT_BLC)
- Lymphocyte count (LBTESTCD=LYMPH_BLC)
- Platelet count (LBTESTCD=PLT_PLC)

In addition to this, the ratio IgG/IgA will be derived and added to the list of labtest in the Analysis and Reporting dataset. The LBTESTCD will be IGG_IGA_RATIO and the derivation will simply be $\text{IgG} \div \text{IgA}$. If either value is missing or lower than LLQ then this ratio will be set to missing.

11.3.7. Salivary Flow Rate

Salivary Flow Rate

Salivary flow rate is measured at basal and stimulated state at screening/baseline and at follow-up.

Mean of baseline and follow-up visit will be calculated separately for stimulated and basal salivary flow rate. The mean will be calculated as:

- Mean Stimulated/Basal salivary flow = $(\text{Stimulated/Basal salivary flow at baseline} + \text{Stimulated/Basal salivary flow at follow-up}) \div 2$.

If value is missing at one time point (e.g. baseline), then the rate from the other time (follow-up) will be used for the mean.

The difference of the stimulate and basal salivary flow rate will be calculated for each time point:

- Screening/baseline difference = Stimulated salivary flow rate at baseline - Basal salivary flow rate at baseline
- Follow-up difference = Stimulated salivary flow rate at follow-up – Basal salivary flow rate at follow-up.

If one of the rate (stimulated or basal) is missing at one time point (e.g. baseline), then the rate

from the other time (follow-up) will be used to calculate the difference. If the measure of the rate is missing at both time points, then difference will be set to missing.

The mean of difference (stimulated-basal) will be derived as follows:

- Mean difference (stimulated – basal) salivary flow = (Screening/baseline difference + Follow-up difference) ÷ 2

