## Follow up

Within 2 weeks of Visit 2 there will be a follow up visit. This may be conducted by telephone for the healthy volunteers (Group A). The pSS subjects (Group B) may have their Follow up visit in person, or by telephone if the Investigator considers it clinically appropriate. Adverse events (AE) will be reviewed at this visit for all of the subjects (Group A and Group B)

The total duration of the study will be up to 11 weeks (14 only if it becomes necessary to delay the minor salivary gland biopsy), although ideally the study should be completed as soon as practicable within the time windows.

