**Table 3 Time and Events Table – Study Assessments**

Procedure	Visit 1	Visit 2	Follow up
	Within 6 weeks after baseline	Within 3 weeks after Visit 1	Within 2 weeks after Visit 2
MRI safety questionnaire 	X		
Vital signs	X	X	
Concomitant medication review	X	X	
Basal salivary flow		X	
Stimulated salivary flow (including saliva collection)		X	
Schirmer's test (including tear collection)		X	
Plasma metabolomics/proteomics		X	
Urine pregnancy test (FRP)	X 	X 	
Multi-parametric MRI scan (including contrast)	X		
Meal prior to  C-MET PET/CT	X		
Intravenous injection of  C-MET PET tracer	X		
 C-MET PET/CT scan (dynamic and static)	X		
Radio-PK (  C-MET) sampling (dynamic scan)	X 		
Measure concentration of  C-MET tracer in blood	X 		
Blood glucose (bedside glucometer)	X 		
Injection of  F-FDG tracer	X 		
 F-FDG PET/CT scan	X 		
Measure concentration of  F-FDG in blood	X 		
Salivary gland biopsy		X 	
AE review		X	

AE = adverse event; CT = computed Tomography; FDG = flurodeoxyglucose; FRP = females of reproductive potential; FSH = follicle stimulating hormone; MET = methionine; MRI = magnetic resonance imaging; PET = positron emission tomography; PK = pharmacokinetics.

1. Females of reproductive potential only

2. Radio-PK sampling (5mL per sample) to be taken at 1, 2, 5, 10, 15, 20, 30 and 40 minutes after injection of C-MET PET tracer (number and sampling times are subject to change dependent on emerging data, but no more than 100 mL overall will be taken).
3. To be taken within 5 minutes after the static PET/CT scan (exact time to be recorded).
4. pSS subjects only. If it is not possible to schedule the minor salivary gland biopsy within the 3 week window after Visit 1, this procedure may be performed up to 6 weeks after Visit 1, subject to prior agreement of the medical monitor.
5. The MRI safety questionnaire will not be databased.

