2.3. Study Design

Overview of Study Design and Key Features	
	
Events Table).
 
 • Visit 2 should occur within 3 weeks after Visit 1. Visit 2 will involve measurement of basal and stimulated (chewing paraffin) salivary flow rate (including saliva collection), Schirmer’s test (including tear collection), and blood samples for metabolomics/proteomics. In addition, a minor salivary gland biopsy will be performed on the pSS subjects (Group B). • Visit 1 and Visit 2 may be split over more than one day.
Contrast	
 • ¹⁸F-FDG (Group B only) radiotracer injected prior to PET/CT scanning. • ¹¹C-MET radiotracer injected prior to PET/CT scanning. • Gadoterate meglumine (Dotarem®) contrast agent administered prior to MRI scanning
Tracer Assignment	
 • All subjects will undergo MRI and ¹¹C-MET PET/CT at study visit 1. • pSS subjects (Group B) will also undergo ¹⁸F-FDG PET/CT at study visit 1.

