The histological scores (see Section 11.3.5) and the various disease indices (see Section 11.3.4) – ESSDAI, ESSPRI, Patient and Physician global assessment of disease activity, oral and ocular dryness scales will be descriptively summarized and listed for pSS group only.

Descriptive statistics will be calculated for the exploratory multiparametric MRI quantitative derived parameters listed in Table 7 (as data permits) and presented in tables. All parameters will be listed by group (and ROI, as data permits). Mean (\pm SE bars) will be plotted for each parameter by ROI (if appropriate with panel for each side).

Correlation between ^{18}F -FDG PET/CT (pSS subjects only), ^{11}C -MET PET/CT and MRI parameters (HV and pSS subjects) in the region of the salivary glands (parotid gland) will be explored using scatter plots. Plots will be in panel for each side (most vs least uptake) of the region scanned. The parameters will include, SUV_{peak} for PET/CT and K_{trans} , D and f for multiparametric MRI.

Furthermore, correlation between the imaging parameters mentioned above and

- histological scores (mean and maximum lymphoid organisation score and volume fraction) from the minor salivary gland biopsy
- Salivary flow rate – mean (from baseline and visit 2) stimulated and basal salivary flow rate, and mean difference (stimulated – basal)
- Measures of Disease Activity – ESSDAI and ESSPRI scores
- Lab biomarkers of disease activity – C3 and C4 levels
- Schirmer's test – length of paper wetted by eyes (panel for each side; least and most) and time to completely wet the strip (panel for each side; least and most).

may be explored using scatter plots (panel for each side) and statistical analysis summarised in tables. In addition, SUV_{peak} from the ^{11}C -MET PET/CT will be correlated with the ratio of IgG/IgA using scatter plots and summary tables of the correlation. See below for summary of correlations:

CONFIDENTIAL

203818

Method		11C-MET PET/CT	18F-FDG PET/CT	Multiparametric MRI
	Parameter(s)/Endpoint	SUVpeak	SUVpeak	(median) Ktrans, (median) D, (median) ADC, (median) f, (median) IRE, (median) ME, (mean) Lipid Content, (median) D* (pseudo diffusion), (mean) gland volume
11C-MET PET/CT	SUVpeak		Yes	
18F-FDG PET/CT	SUVpeak	Yes		
Multiparametric MRI	(mean) lipid content	Yes	Yes	Yes ¹
Histological scores	Max lymphocyte focus score	Yes	Yes	Yes
	Mean lymphocyte focus score			
	Max Lymphoid organisation grading			
	Mean Lymphoid organisation grading			

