11.4.2.3. Handling of Missing Data for Statistical Analysis

Missing data will remain missing with no imputation applied for the purposes of statistical analysis.

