11.11.10. Biomarker Tables

Biomarker: Tables					
No.	Population	IDSL / TST ID / Example Shell	Title	Programming Notes	Deliverable [Priority]
Disease Activity (pSS only)					
5.1.	Safety	EFF_T2	Summary of Disease Activity	List score in the following order: ESSDAI ESSPRI PtGA PhGA Oral dryness Ocular dryness	SAC
5.2.	Safety	EFF_T7	Frequency of ESSDAI Component Scores	Footnote: NA: Not Applicable – Not given as an option for the category in the questionnaire.	SAC

Biomarker: Tables					
No.	Population	IDSL / TST ID / Example Shell	Title	Programming Notes	Deliverable [Priority]
5.3.	Safety	EFF_T3	Summary of Correlation Between Disease Activity and Imaging Parameters	
Paginate by type of Disease Activity scores.
 
Disease activity score include: ESSDAI and ESSPRI scores
 
Pearson's and Spearman's correlation summary to be provided in the summary table.
 
Imaging parameter from the parotid gland, and include variable for side (high or low, or aggregated).
 
PET/CT parameter: SUVpeak
 
MRI parameter: Median Ktrans, D, IRE, ME, f, ADC, D*; Mean lipid content and gland volume.
 
Subheading 'Disease Activity: [name]'
	SAC
5.4.	Safety	EFF_T2	Summary of Laboratory Biomarkers of Disease Activity	
Including but not limited to, SS-A, SS-B, C3, C4, CH50, CRP, cryoglobulins, RF, Immunoglobulins, protein electrophoresis. See 11.3.6 for full list.
	SAC

Biomarker: Tables					
No.	Population	IDSL / TST ID / Example Shell	Title	Programming Notes	Deliverable [Priority]
5.5.	Safety	EFF_T3	Summary of Correlation Between Laboratory Biomarkers of Disease Activity and Imaging Parameters	Paginate by Laboratory biomarker type. Lab biomarkers: C3, C4 levels and IgG/IgA ratio. Pearson's and Spearman's correlation summary to be provided in the summary table. Imaging parameter from the parotid gland, and include variable for side (high or low, or aggregated). PET/CT and MRI parameter: see Table 5.3 Subheading 'Laboratory Biomarker: [name]'	SAC
Salivary gland					
5.6.	Safety	EFF_T2	Summary of Basal (unstimulated) and Stimulated Salivary Flow Rate (ml/min)	Replace first column with 'Salivary Flow' and add second column 'Group'. Salivary Flow column will include Basal, Stimulated and Difference. Footnote1: 'Difference for each individual calculated as stimulated-basal salivary flow at that time point.' Footnote2: 'Salivary flow rate measured in millilitres per minute (ml/min).'	SAC

Biomarker: Tables					

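### SAP 11.3.7 names the wrong second visit for salivary flow, and its gap-filling rule can subtract rates taken at different visits

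*SAP*

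**What the plan says.** SAP 11.3.7 opens with "Salivary flow rate is measured at basal and stimulated state at screening/baseline and at follow-up". It then defines four things from baseline and follow-up values: mean basal flow, mean stimulated flow, a stimulated-minus-basal difference at each of the two time points, and the mean of those differences. Visit 2 is not mentioned in the section.

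It has two rules for gaps. For the means: "If value is missing at one time point (e.g. baseline), then the rate from the other time (follow-up) will be used for the mean". For the differences, a rate that is absent at one time point is taken from the other, and the difference becomes missing only if that rate is absent at both.

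Other parts of the plan read differently:

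- SAP 2.3: "Visit 2 will involve measurement of basal and stimulated (chewing paraffin) salivary flow rate (including saliva collection"). Protocol Tables 2 and 3 and the schedule in SAP Appendix 1 agree. Flow is marked at Screening/Baseline and Visit 2, with no entry under Follow up.
- SAP 9.1.1 defines the variable to be correlated with imaging as the "mean (from baseline and visit 2) stimulated and basal salivary flow rate".
- The footnote to SAP Tables 5.6 and 5.7: "Difference for each individual calculated as stimulated-basal salivary flow at that time point".
- SAP 11.4.2.3: "Missing data will remain missing with no imputation applied for the purposes of statistical analysis".

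**The concern.** There are two separate faults.

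**Wrong visit.** The section that programmers work from points to a contact at which flow is never measured. Protocol 4.2 places Follow up within two weeks after Visit 2 and allows it by telephone in both groups. Sections 9.1.1 and 11.3.7 cannot both be followed as written. The measurement at risk is also the one closer to the scans: screening flow may precede Visit 1 by up to six weeks, while Visit 2 flow falls within three weeks after it. The six-week extension applies to the biopsy alone.

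**Mixed visits.** This remains after the label is corrected. If one rate is missing at a visit, the difference for that visit combines a stimulated rate from one day with a basal rate from another. Any change in flow between visits is then counted as part of the gap between stimulated and basal flow, under a footnote saying that both were taken at one time point.

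Flow is one of several clinical measures set against the imaging parameters (SAP Table 5.7, Figures 5.1 to 5.3). Those correlations are tabulated by group, with 8 to 12 pSS subjects and 4 to 12 healthy volunteers, so one odd value can move an estimate.

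**Working it through.** The plan gives no figure to reproduce here. The first step sets the texts side by side; the remaining steps are illustrations on invented values or declared assumptions.

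**Step 1. Which visit?** Follow up in 11.3.7 cannot mean the scheduled Follow up contact, because no flow is collected there. The only second flow measurement in either document is at Visit 2. The neighbouring SAP 11.3.8, on Schirmer's test, names Visit 2 correctly, so follow-up is not a SAP shorthand for Visit 2.

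**Step 2. The literal rule.** Take an invented subject (mL/min): baseline basal 0.10 and stimulated 0.60; Visit 2 basal 0.30 and stimulated 1.00.

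- Read as Visit 2: mean basal (0.10 + 0.30)/2 = 0.20; mean stimulated (0.60 + 1.00)/2 = 0.80; mean difference (0.50 + 0.70)/2 = 0.60.
- Read literally: both follow-up rates are absent and are filled from baseline, giving 0.10, 0.60 and 0.50. These are the baseline values, and the same happens for every subject.

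**Step 3. Cost of one visit instead of two.** Assume a within-subject ICC *r* between visits (not in the documents). Reliability is *r* for one visit and 2*r*/(1 + *r*) for the two-visit mean. The expected correlation with imaging is multiplied by the square root of their ratio.

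- *r* = 0.6: reliability 0.60 against 1.2/1.6 = 0.75; √(0.60/0.75) = 0.894, a shrinkage of about 11%.
- *r* = 0.8: reliability 0.80 against 1.6/1.8 = 0.889; √(0.80/0.889) = 0.949, a shrinkage of about 5%.

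**Step 4. The mixed difference.** Use the same subject, with follow-up now read as Visit 2 and one rate removed.

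| Missing rate | Filled difference | Mean difference under 11.3.7 | Complete visit alone |
|---|---|---|---|
| Visit 2 stimulated | 0.60 − 0.30 = 0.30 | (0.50 + 0.30)/2 = 0.40 | 0.50 |
| Baseline basal | 0.60 − 0.30 = 0.30 | (0.30 + 0.70)/2 = 0.50 | 0.70 |
| Baseline stimulated | 1.00 − 0.10 = 0.90 | (0.90 + 0.70)/2 = 0.80 | 0.70 |

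The error can go either way. If a whole visit is missing, both rates come from the other visit and the result is that visit's own difference, so nothing is mixed. SAP 11.3.8 substitutes by component in the same way, which supports this reading of the rule.

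**Step 5. Is a mixed difference noisier?** Let ρ be the correlation, within a visit, between the visit-to-visit deviations of basal and stimulated flow, with equal variances. The within-subject variance of a cross-visit difference is then 1/(1 − ρ) times that of a same-visit difference: 1.0, 1.43, 2.0 and 3.33 for ρ = 0, 0.3, 0.5 and 0.7. The documents give no value for ρ.

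**The case against.** The strongest reply is that nobody would be misled. The SAP names Visit 2 as the second flow measurement in its design section, in its own schedule and in the definition of the correlated variable. To lose Visit 2, a programmer would have to find the second time point empty in every subject, fill it in all of them and disregard 9.1.1. This stands. A reader might infer from 11.3.7 that the plan discards the Visit 2 measurement; the documents do not support that, and the label is an error to correct.

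The shrinkage in Step 3 belongs only to that unlikely reading and is small beside the sampling error. At n = 12 and r = 0.50, the Fisher 95% interval runs from about −0.10 to 0.83, while the shrinkage moves r to about 0.45 to 0.47. This also stands.

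On the mixed difference, the reply is that it needs exactly one of two rates missing at a visit where both are scheduled, and that baseline flow is assessed for eligibility in pSS subjects. The case is therefore probably uncommon, and no frequency can be given. It may also be said that 11.3.7 is a specific prespecified rule, echoed in 11.3.8, and so governs over the general statement in 11.4.2.3. That weakens the conflict with 11.4.2.3. It does not remove the conflict with the footnotes to Tables 5.6 and 5.7, which describe a same-visit quantity.

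A reader might also infer that filled values will appear as observed results in a by-visit summary. The shell for Table 5.6 has no visit column and its programming note adds none, so that is not shown.

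**Conclusion.** The concern holds as a correction to a derivation rule. Section 11.3.7 names a time point at which flow is not measured and contradicts 9.1.1 and both schedules. On its plain reading, it also forms a difference across visits when exactly one rate is missing, contrary to the table footnotes and at odds with 11.4.2.3.

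The reach is narrow. Only the exploratory flow-imaging correlations and the flow summaries are affected; the primary imaging analyses and the secondary radio-pharmacokinetic analyses are not. The size cannot be settled from the documents. The 5 to 11% shrinkage rests on an assumed ICC of 0.6 to 0.8 and arises only if the wrong label is followed literally. For the mixed difference, neither the frequency nor the variance penalty is known, so it should not be claimed that a mixed difference is always the noisier one.

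**What to change.** Before database freeze:

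1. Replace follow-up with Visit 2 throughout SAP 11.3.7.
2. Compute the stimulated-minus-basal difference only within a visit that has both rates.
3. Take the mean difference over the complete visits available, one or two.
4. State in 11.4.2.3 that using the single available visit is the defined derivation, so that the two sections agree.

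The cost is a change of SAP wording and derivation code. An occasional per-visit difference will be missing where it would have been filled. In a subject with one missing rate, the mean difference need not equal mean stimulated minus mean basal flow: in the first row of the Step 4 table it would be 0.50, against 0.60 − 0.20 = 0.40. A footnote saying so is enough.
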